#### 2. Objectives

##### Primary Objectives

**Aim 1. Establish the safety and tolerability of bile acid supplementation and determine whether this intervention leads to normalization of the bile acid profile in people with progressive MS with abnormal bile acid metabolism**

*Hypothesis: Bile acid supplementation is safe and tolerable and will help normalize the bile acid profile in people with MS.*

**Method:** In a randomized, double-blind, placebo-controlled, phase 1/2 study of bile acid supplementation in people with progressive MS with abnormal bile acid metabolism, we will establish the safety and tolerability of this intervention and evaluate its effects on bile acid profiles as determined by targeted metabolomics.

**Aim 2. Assess the effects of bile acid supplementation on the gut microbiota and the peripheral immune system in people with MS**

*Hypothesis: Bile acid supplementation leads to alterations in the gut microbiota and peripheral immune system in people with MS.*

[figure not shown]
**Method:** We will determine the change in gut microbiota composition following bile acid supplementation and determine changes in peripheral immune cell function in participants enrolled in the phase 1/2 trial of bile acid supplementation mentioned in Aim 1.

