**c. Statistical plan including sample size justification and interim data analysis.**

Safety data will be analyzed as they are captured in real time. Assessments will focus on AEs (including study treatment tolerability assessments, laboratory evaluations, vital signs and physical examination). The incidence rate of AEs will be recorded by system organ class, severity and by relationship to study treatment. Tolerability analysis will be based on the number (%) of participants who failed to complete the study due to adverse events. Lab values for each parameter will be summarized by shift tables. For quantitative parameters, we will present summary statistics for actual values and change from baseline. We will compare changes over the 16-week treatment period between the groups using mixed effects regression analyses to account for repeated measures using random subject-specific intercepts and slopes.

Metabolomics data will be analyzed at the end of the study following quantitation of the 15 bile acids included in our panel. Summary statistics will be used to characterize these outcomes. We will then assess normality of these measures and perform appropriate univariate testing to determine which bile acids are significantly altered by TUDCA supplementation. A mixed effects longitudinal model will also be used to test which bile acids are altered between visits across the two groups. Models will also adjust for important covariates including BMI, age, gender and measures derived from the food frequency questionnaire.

Gut microbiota data, *a priori* analyses will assess changes in relative abundances of different gut bacteria as well as microbial genes that encode bile acid metabolizing enzymes (identified from the literature and NCBI Gene database) which occur as a result of TUDCA treatment. Exploratory analysis will assess the effects of TUDCA on the metagenome using a combination of pathway and set-based approaches previously applied in metagenomics analysis of MS and other diseases to identify other biologically relevant changes[41]–[43].

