Immunophenotyping data, we will summarize data using summary statistics (mean and standard deviation), before and after study treatment. We will utilize paired *t* tests to compare proportions of various immune cell sub-populations at different time points. For both sets of data we will utilize mixed-effects regression models to assess the change in bacterial taxa/ metagenomics pathways/ immune cell subsets over time, and determine their relationship to changes in bile acid concentrations with TUDCA supplementation.

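### The Aim 2 microbiome and immune-cell analyses test an unstated number of features with no multiplicity control, and the immune subsets are compared between time points rather than between arms

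*Combined protocol and SAP*

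**What the plan says.** Section 2 lists Aim 2 under the same heading as Aim 1. Its hypothesis reads "Bile acid supplementation leads to alterations in the gut microbiota and peripheral immune system in people with MS". It names no direction, taxon, gene or cell subset, and gives no criterion for calling the hypothesis supported. Section 7a makes safety and tolerability the primary outcome, and Section 7b lists microbiota and immunophenotyping as secondary.

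Section 7c sets out the analyses in three layers:

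- **Microbiome, labelled a priori.** The "analyses will assess changes in relative abundances of different gut bacteria as well as microbial genes that encode bile acid metabolizing enzymes". The genes are to be "identified from the literature and NCBI Gene database"; neither the list nor its length is given.
- **Microbiome, labelled exploratory.** "Exploratory analysis will assess the effects of TUDCA on the metagenome using a combination of pathway and set-based approaches". Among the microbiome analyses, only this one carries the exploratory label.
- **Immune cells.** Paired t tests are planned "to compare proportions of various immune cell sub-populations at different time points". For both data sets, mixed-effects models will then "assess the change in bacterial taxa/ metagenomics pathways/ immune cell subsets over time" and relate those changes to the bile acid changes.

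The schedule table in Section 4a collects stool and PBMCs at weeks 0, 8 and 16. No section states a multiplicity adjustment, a false-discovery rate or a global test. A significance level of 0.05 appears once, in the sample size paragraph, for a single bile acid.

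**The concern.** There are two linked problems.

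First, the families are open-ended. When many features are each tested at a conventional level, some will cross it by chance. Nothing in the plan limits how many, or lets a reader separate them from real effects. The a priori label matters, because a reader will give listed taxa and genes more weight than findings marked exploratory.

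Second, a paired t test between visits asks whether a subset changed over time, not whether it changed more on TUDCA than on placebo. Drift, diet and assay batch can all move a subset in both arms. The mixed model for taxa and subsets is described as modelling change over time, again without naming the arm contrast. For the bile acids, by contrast, the same section does refer to comparison across the two groups.

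Section 4e justifies the placebo arm by the need to attribute microbiota and immune changes to TUDCA, and says the results would inform whether larger trials are worth pursuing. What is at stake is the list of features carried forward, not the safety conclusion.

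**Working it through.** **The plan's own figure.** No error rate is stated for the Aim 2 analyses, so there is none to reproduce. The nearest figure is the recruitment target: 27 / (1 − 0.10) = 30 per arm, which matches. The lower and upper requirements of 14 and 27 are consistent with each other for a standard deviation of about 0.61 on the scale of the change, but that standard deviation is back-solved, not stated.

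**Inputs for the check**

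- Level per test: 0.05 two-sided. This is an assumption; Section 7c gives it only for the bile acid sample size.
- Number of tests m: not stated, so a range is shown.
- True effect: none.

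**Independent tests.** P(at least one false positive) = 1 − 0.95^m, and the expected number of false positives is 0.05 × m.

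| m | P(at least one) | Expected number |
|---|---|---|
| 10 | 40.1% | 0.5 |
| 20 | 64.2% | 1.0 |
| 50 | 92.3% | 2.5 |
| 100 | 99.4% | 5.0 |

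Reaching 95% takes 59 independent tests; reaching 99% takes 90.

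**Correlated tests.** Relative abundances and cell proportions are unlikely to be independent. Simulating m equally correlated two-sided z tests (40,000 replicates) gives:

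| m | r = 0.3 | r = 0.5 | r = 0.8 |
|---|---|---|---|
| 20 | 54% | 42% | 23% |
| 100 | 95% | 78% | 36% |

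**A hit needed in both domains.** The hypothesis names microbiota and immune system together. For independent tests, the chance is the product of the two domain probabilities:

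- 10 microbiome + 10 immune: 0.401 × 0.401 = 16%
- 50 + 20: 0.923 × 0.642 = 59%
- 100 + 50: 0.994 × 0.923 = 92%

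**Layering.** Three sampling times allow up to three pairwise t tests per immune subset, before the mixed model is fitted to the same data. These tests share data, so they add to m but not as independent tests.

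**After the fix.** When no feature in a family has a true effect and tests are independent, Benjamini-Hochberg at 5% gives a 5% chance of any declared feature in that family, whatever m is. Across three independent families the chance that at least one declares something is 1 − 0.95³ = 14.3%. That is why each family's result should be read on its own.

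**The case against.** The strongest reply is that Aim 2 has no confirmatory role. Its endpoints are secondary outcomes in what Section 7c itself describes as mainly a safety study, and they are meant to inform later trials. Calling an analysis a priori may mean only that the target was chosen in advance, as with the restriction to bile-acid-metabolising enzymes. The count of features, the threshold and the success rule used to show inflation are all supplied from outside the plan, and independence is the least favourable case.

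Much of this stands. A reader might infer that Aim 2 is nearly certain to look confirmed, that it can hardly fail, or that any single nominal hit would count as support. The documents do not support those readings. They give no feature count, set no threshold for these tests and state no rule for declaring Aim 2 met. With 10 to 30 independent tests the chance is 40% to 79%, and with 100 tests correlated at 0.8 it is 36%. The hypothesis also names two domains, so one hit in one domain need not satisfy it.

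The gap itself remains. The reply explains why the consequence is limited, but it does not provide any error control. Every scenario calculated is well above 5%; the lowest is 16%. Nor does it answer the second problem, that a paired t test between visits does not isolate the effect of TUDCA.

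**Conclusion.** The concern holds in a limited form. The a priori taxon and gene analyses and the immune-subset analyses have no multiplicity control, and for the immune subsets the named test is within-participant change rather than a difference between arms. At an assumed 0.05 per test, the chance of at least one false positive under no effect runs from 64% (20 tests) to 99% (100 tests) if independent. At a pairwise correlation of 0.5 it is about 42% to 78%. It is lower again if both domains must be positive. The size depends on the number of features, their correlation and the threshold, none of which the plan states.

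The primary safety conclusion does not depend on any of this. The practical consequence is that a list of taxa and subsets attributed to TUDCA would contain a share of false positives that no reader could estimate.

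**What to change.** Before unblinding, amend Section 7c as follows:

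1. Fix three families: taxa above a stated prevalence cut-off, a listed set of bile-acid-metabolising genes, and a listed set of immune subsets.
2. For each feature, make the between-arm treatment-by-visit effect from the mixed model already planned the test of the TUDCA effect. Keep the paired t tests as description only.
3. Apply Benjamini-Hochberg at 5% within each family, and report unadjusted results as exploratory.
4. Optionally, add a global test per domain, chosen to suit it. A permutation test on community distance fits the microbiota but not the immune subsets. If global tests are used, state whether one or both domains must be positive to support Aim 2.

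This needs SAP wording and a little code, with no new participants, samples or visits. The real cost is power, with about 27 evaluable participants per arm (30 × 0.9). In the hardest case, where only one feature in a family truly changes, it must roughly meet 0.05/m: 0.0025 for 20 features and 0.0005 for 100. At 85% power the detectable effect scales with z(1 − α/2) + z(0.85). That sum is 1.960 + 1.036 = 2.996 at 0.05, 3.023 + 1.036 = 4.060 at 0.0025 (after rounding), and 3.481 + 1.036 = 4.517 at 0.0005. The lone effect would have to be about 35% larger (4.060 / 2.996) or 51% larger (4.517 / 2.996). The penalty shrinks when several features change together, because Benjamini-Hochberg then relaxes the threshold. Short, well-chosen families keep it down.

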**e. Justification for inclusion of a placebo or non-treatment group.**

While this trial is primarily focused on establishing the safety and tolerability of TUDCA in patients with progressive MS, the inclusion of a placebo group will enable us to determine whether changes observed in serum bile acid profiles, gut microbiota, immunophenotype and clinical/ quality of life measures are related to TUDCA treatment. This would provide information regarding the utility of pursuing larger trials focused on clinical outcomes in this patient population.

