**b. Secondary outcome variables.**

1. Metabolomics – We will store plasma before and after the study intervention to assess the effect of the study medication on fasting bile acid levels. This will enable us to determine whether the study drug raised the levels of bile acids that were deficient in people with MS. Targeted metabolomics analyses will be performed through Metabolon Inc.
2. Gut microbiota – The composition of the gut microbiota is closely related to bile acid metabolism, and alterations in bile acid receptor (FXR) signaling can significantly affect composition of the gut microbiota[37],[38]. We will collect first morning stool specimens prior to and following study treatment to determine the effect of bile acid supplementation on the gut microbiota in people with MS.
3. Immunophenotyping – We will store PBMCs from before and after the study intervention to assess the effect of TUDCA supplementation on the peripheral immune system. Our laboratory has expertise in immunophenotyping people with MS and assessing the effect of

therapeutic interventions on peripheral immune cell function. These assays will be performed at the end of the study.

4. Other outcomes – We will also collect information regarding quality of life using the MSQOL-54 instrument[39] administered at the visits noted in the table above. We will also measure lipid profile and hemoglobin A1c at baseline and end-of-study, since bile acid metabolism is linked to obesity and metabolic syndrome.

Assessment of important covariates: We will collect demographic information including age, gender, cigarette smoking, waist circumference, and BMI which can affect circulating bile acid levels. Another critical factor that can affect bile acid metabolism and the gut microbiota is diet. Since TUDCA could potentially lead to GI side effects, this may result in a change in diet. To monitor changes in diet we will perform the Block Food frequency questionnaire before and after the study intervention. Since antibiotics and probiotics can lead to changes in the gut microbiome and could also affect bile acid metabolism, we will collect detailed information on the use of both these covariates so they can be adjusted for in our final analyses.

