#### Sample size justification

Since this is primarily a safety study we based our sample size on the ability to detect changes in our secondary outcomes, especially metabolomics. Previous studies of supplementation of UDCA and TUDCA have resulted in alterations in the total serum bile acid levels (2-8 fold change) and the composition of the bile acid pool. Based on our preliminary data, to detect a 50 - 70% change in levels of an individual bile acid, with a power of 85% and two-tailed alpha of 0.05 the required sample size would be between 14 – 27 in each arm. Accounting for a 10% drop-out rate, we will aim to recruit 30 participants in each arm of the trial. We have previously noted significant alterations in metabolic profiles in MS patients treated with vitamin D and dimethyl fumarate in studies utilizing between 18-24 patients (as shown in preliminary data).

From a safety stand-point, a sample size of 30 would enable us to conclude with 80% confidence that the rate of occurrence of serious adverse events with TUDCA treatment was less than 5% if none of the patients experienced a serious adverse event during the study[40].

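### Immune-cell subsets are tested by paired t tests between visits, which cannot attribute change to TUDCA, and the immune and microbiome mixed models state no arm contrast

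*Combined protocol and SAP*

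**What the plan says.** Section 7c gives the immunophenotyping analysis in three steps. Data are summarised before and after treatment. Paired *t* "tests to compare proportions of various immune cell sub-populations at different time points" follow. Mixed-effects models, shared with the microbiota data, then assess change over time and "determine their relationship to changes in bile acid concentrations with TUDCA supplementation". None of the three steps mentions arm, group, placebo or a treatment-by-visit term, and the text does not say whether the paired tests are run by arm or on both arms pooled.

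For the microbiota, 7c plans to assess changes "which occur as a result of TUDCA treatment" but names no model term that would isolate them.

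Elsewhere the same section does state the comparison. For quantitative safety parameters: "We will compare changes over the 16-week treatment period between the groups using mixed effects regression analyses". For bile acids, a longitudinal mixed model is "used to test which bile acids are altered between visits across the two groups".

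The purpose of these outcomes is also stated. Section 7b says the immune assays are there to "assess the effect of TUDCA supplementation on the peripheral immune system". Section 4e says that "the inclusion of a placebo group will enable us to determine whether changes observed in serum bile acid profiles, gut microbiota, immunophenotype" and clinical measures are related to the drug.

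**The concern.** Aim 2 is a causal question: does TUDCA alter the gut microbiota and the peripheral immune system? Section 4e gives answering it as the reason for a placebo group.

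A paired test between visits compares participants with themselves. Run in the TUDCA arm, it uses no placebo data; run on both arms pooled, it averages over treatment. Neither version separates a drug effect from a change that would have happened on placebo.

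The association with bile acid change does not fill the gap. Bile acid change is measured after randomisation, so relating immune or microbial change to it is not a randomised comparison.

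Two things are at stake. A shared change in an immune subset could be reported as an effect of TUDCA. And because the between-arm contrast for immune, taxon and pathway outcomes is not written down, it could be chosen after the data are seen. The two halves of the point differ in weight: the immune paired test is the wrong test for the question, whereas for taxa and pathways the only defect is the unstated model term.

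**Working it through.** **1. What each analysis in 7c contrasts**

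| Outcome | Stated analysis | TUDCA versus placebo stated? |
|---|---|---|
| Safety parameters | Mixed model of change over 16 weeks | Yes |
| Bile acids | Longitudinal mixed model | Yes |
| Immune subsets | Paired *t* tests between time points | No |
| Immune subsets | Mixed model: time, relation to bile acid change | No |
| Taxa and pathways | Mixed model: time, relation to bile acid change | No (intent only) |

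**2. Inputs**

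- From the sample size justification: 30 recruited per arm, 10% drop-out, two-sided alpha 0.05, power 85%. Completers per arm: 30 × 0.9 = 27. This agrees with the plan's own step, 27 / 0.9 = 30. That sizing is for individual bile acids; the plan gives no power figure for immune or microbiota outcomes, so there is none to reproduce.
- Assumed: TUDCA has no effect, and both arms change by the same amount *d*, in units of the SD of within-person change. The documents give no value of *d*, so a range is shown.

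**3. How often the paired test is significant when the drug does nothing**

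The paired statistic follows a noncentral *t* distribution with *n* − 1 degrees of freedom and noncentrality *d*√*n*. The rejection probability is

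*p* = P(*T* > *t*₀.₉₇₅) + P(*T* < −*t*₀.₉₇₅).

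Example: *n* = 27 and *d* = 0.4 give noncentrality 0.4 × √27 = 2.08 against a critical value of 2.056 on 26 df, so *p* = 0.517.

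If the tests are run by arm and a drug effect is declared when TUDCA is significant and placebo is not, that occurs with probability *p*(1 − *p*), because the arms are independent. The documents do not state this rule; it is one way the tests might be read.

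| Common change *d* | TUDCA arm, n = 27 | Pooled, n = 54 | TUDCA significant, placebo not | Between-arm test |
|---|---|---|---|---|
| 0 | 5% | 5% | 5% | 5% |
| 0.1 | 8% | 11% | 7% | 5% |
| 0.2 | 17% | 30% | 14% | 5% |
| 0.3 | 32% | 58% | 22% | 5% |
| 0.4 | 52% | 82% | 25% | 5% |
| 0.5 | 71% | 95% | 21% | 5% |
| 0.8 | 98% | >99% | 2% | 5% |

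The between-arm column holds by construction: a change common to both arms cancels from the difference. Simulation with 27 per arm gave 0.049 to 0.050.

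**4. What the between-arm test costs in sensitivity**

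Smallest effect detectable at 85% power, two-sided 0.05:

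- paired test in one arm, *n* = 27: 0.60 SD of change;
- two-sample test on change, 27 per arm: 0.83 SD of change, before any precision gained from baseline adjustment.

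**The case against.** The strongest reply is that the arm comparison is implied. This is a two-arm randomised placebo-controlled trial, section 4e says what the placebo group is for, 7c speaks of changes resulting from TUDCA, and a mixed model is planned for exactly these data. On that reading the paired tests are a descriptive first step and the arm term is merely unwritten. For taxa and pathways this is largely right, and the point there is only missing detail. It does not rescue the immune plan: the paired test is the only hypothesis test named specifically for immune subsets, nothing labels it descriptive, and the same section writes out the group comparison where it covers safety parameters and bile acids.

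A second reply is that the error rates depend on a common change the documents do not supply. That is true: at 0.1 SD the TUDCA-arm test rejects only 8% of the time. Some sources of drift are also limited by design. Immune assays are run at the end of the study (7b), and eligibility requires stable therapy and excludes recent relapse, recent corticosteroids and chronic antibiotics (section 5). Nor is anyone selected on an immune value, so regression to the mean has no obvious source. These features reduce a shared change but do not rule it out, and the figures are an illustration, not an expected error rate.

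Third, relating immune or microbial change to bile acid change is a legitimate mechanistic question. That stands, provided it is not used as the test of treatment effect.

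Finally, these are secondary outcomes in a study whose primary outcome is safety and tolerability, and the sample size was computed for bile acids. That limits the weight of the point, but these outcomes are the whole of one of the trial's two aims.

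**Conclusion.** The concern holds. For immune subsets the stated paired test is wrong for the question, because it makes no use of the placebo comparison. For taxa and metagenomic pathways the defect is narrower: the arm term in the mixed model is not stated.

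The size depends on an assumed change common to both arms. With 27 completers per arm and no drug effect, a common change of 0.2 to 0.5 SD makes the TUDCA-arm paired test significant 17% to 71% of the time, or 30% to 95% if the arms are pooled, against 5% for a between-arm test. With no common change there is no inflation. These figures apply to the immune paired tests only. This should be fixed before the data are analysed; it does not affect the primary safety outcome.

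**What to change.** In the immunophenotyping text of section 7c:

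- Make the difference between TUDCA and placebo in change from baseline the test for immune subsets. Use either the arm-by-visit term of the planned mixed model (baseline, week 8, week 16) or a baseline-adjusted ANCOVA, and name which.
- State the same arm-by-visit term for taxa and metagenomic pathways.
- Label the paired *t* tests descriptive, and say whether they are reported by arm.
- Label the associations with bile acid change exploratory.

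The cost is wording. Placebo samples, the visits and the mixed model are already planned. The downside is sensitivity: the detectable effect rises from 0.60 to about 0.83 SD of change, and baseline adjustment may recover part of that. The smaller figure was never a detectable drug effect, since it belongs to a test that does not compare the arms.
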